2.1.2 Analysis visit windows

Analysis visit windows will be used for the data that is summarized by visit; they are based on the study evaluation schedule and comprise a set of days around the nominal visit day. For any assessment, there are the protocol defined scheduled visits around which visit windows will be created to cover the complete range of days within the study. These visit windows apply to measurements taken at every visit. For assessments collected less often different visit windows will be applied as detailed below.

The analysis visit windows depend on the visit schedule for the assessments and are shown in [Table 2-1](#).

The analysis visit will be used for listing of visit and period.

The mapping described above applies to all visits (not just scheduled visits). Repeat and/or unscheduled visits (which will be numbered in the database according to new NCDS standards) will be mapped for analysis purposes in the same way as scheduled visits. This leaves the possibility, then, for multiple measurements within an analysis window. The conventions in [Table 2-2](#) will be used to determine the appropriate measurement to be summarized in the event of multiple measurements within a visit window.

Table 2-1 Analysis visit windows

Analysis Visit	Week	Scheduled Day	Variables assessed everyVisit		weight, ECG	Vital signs, LAB	PK	Visit window (Day)		Lipids	Cardiovascular panel
			ASQoL, SF-36	Immunogenicity							
Baseline		BSL	1	to 1	to 1	to 1	to 1	to 1	to 1	to 1	to 1
Week 1	1	8	2-11		2-11						
Week 2	2	15	12-18		12-18						
Week 3	3	22	19-25		19-25						
Week 4	4	29	26-43		26-43	2-71	2-43				
Week 8	8	57	44-71		44-71		44-71			2-85	
Week 12	12	85	72-99		72-99		72-99				
Week 16	16	113	100-127	2-239	100-127	72-141	100-141	2-141		86-239	2-141
Week 20	20	141	128-155		128-155						
Week 24	24	169	156-183		156-183	142-267	142-267	142-267			142-267
Week 28	28	197	184-211		184-239						
Week 32	32	225	212-239								
Week 36	36	253	240-267								
Week 40	40	281	268-295		240-323						
Week 44	44	309	296-323								
Week 48	48	337	324-351								
Week 52	52	365	352-393	240-393	324-393	268-393	268-393	268-393		240-393	268-393
Week 60	60	421	394-449	CRF visit	CRF visit	394-449	394-449	394-449		-	-

Variables assessed every visit: Patient's global assessment of disease activity (VAS), Patient's assessment of back pain intensity (VAS), BASFI, BASDAI, Spinal mobility (BASMI Linear + chest expansion), [REDACTED], hsCRP

Note that safety assessments in Week F60 in the post treatment follow-up period will NOT be mapped to Week 1 – Week 52 of Analysis Visits

Table 2-2 Rules for flagging variables

Timing of measurement	Type of data	Rule
Baseline	All data	The last measurement made prior to administration of the first dose of study treatment. Baseline assessments scheduled for and captured on day 1 will be considered baseline measurements regardless of the time of assessment. In case several measurements are taken on day 1 after the first dose of study treatment, the first one will be used.
Post-baseline efficacy	All data	The measurement closest to the target will be used. In the event two measurements are taken equally apart (e.g. 1 before target date and 1 after) the first one will be used.
Post-baseline safety	Summary visit information (e.g. lab, ECG, etc.)	
Post-baseline safety	Notable abnormalities (e.g. lab)	The most extreme measurement in the window will be used. Note this means a patient can have a notably high and notably low measurement within a window.

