## 6.5 Safety

- T-SPOT test or PPD skin test
- Chest x-ray or MRI
- Physical examination
- Vital signs
- Height and weight
- Laboratory evaluations
- Hepatitis B, C and/ or HIV serology
- Immunogenicity
- Electrocardiogram
- Pregnancy and assessment of fertility
- Local tolerability (Injection site reactions)
- Tolerability of secukinumab

All blood draws and safety assessments should be done prior to study treatment administration. Appropriate safety assessments (e.g., evaluation of AEs and SAEs including injection site reactions) should be repeated after the dose is administered.

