### **6.6.5 Pharmacokinetics (PK)**

PK samples will be obtained for all patients. Secukinumab concentrations will be assessed in serum. The PK samples will be collected pre-dose at scheduled visits as indicated in [Table 6-1](#). The Pharmacokinetics Sample Log can be found in the [Appendix 2](#). All blood samples will be taken by direct venipuncture in a forearm vein.

The actual sample collection date and exact time will be entered on the PK blood collection summary page in the eCRF.

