**Table 13-3 Blood collection log for pharmacokinetics**

Week	Timepoint	Volume	PK Sample number	PK collection number
BSL	0 (pre-dose)	2 ml	101	1
Week 4	0 (pre-dose)	2 ml	102	2
Week 16	0 (pre-dose)	2 ml	103	3
Week 24	0 (pre-dose)	2 ml	104	4
Week 52	672 h (post-dose)	2 ml	105	5
Week 60	2016 h (post-dose)	2 ml	106	5
Unscheduled*		2 ml	100x**	NA

\* Unscheduled blood sample is obtained based on the decision of investigators.

\*\* Unscheduled blood samples will be uniquely, sequentially numbered 1001, 1002,...

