2.9 Pharmacokinetic endpoints

All patients with concentration data will be included in the pharmacokinetic data analysis.

Pharmacokinetic variables

Serum concentrations will be expressed in mass per volume units. All concentrations below the limit of quantification as well as missing data will be labeled as such in the concentration data listings. PK concentrations will be summarized by visit. In addition to mean, standard deviation (SD), coefficient of variation (CV), median and quartiles, the geometric mean and geometric coefficient of variation (CV) and n(log) will be presented. The formula for deriving the geometric mean and CV (%) is as following:

- $CV (\%) = (SD/\text{mean}) * 100$,
- geometric mean = $\exp((\text{sum of log transformed data}) / (\text{number of non-missing data points after log transformation}))$,
- geometric CV = $\sqrt{\exp(\text{variance of log-transformed data}) - 1} * 100$.

In addition, sample number, concentration, sample date, sample time at pre-dose and minutes pre-dose will be listed. All data will be listed.

Statistical methods for pharmacokinetic analyses

Pharmacokinetic data of the study treatment will be analyzed with a population pharmacokinetic mixed effects model. The analysis will be based on a pooled data set, including pharmacokinetic samples from previous studies. The modeling approach will be further detailed in a modeling plan. Results will be reported separately.

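### An early discontinuer's F60 PK sample, taken 84 days after the last dose, is windowed into the Week 16, 24 or 52 PK summary because the SAP's F60 exclusion covers safety assessments only

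*SAP*

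**What the plan says.** SAP 2.1.2 sets the scope of the windows: "Analysis visit windows will be used for the data that is summarized by visit". It adds that the mapping covers unscheduled and repeat visits as well as scheduled ones. SAP 2.9 brings PK within that scope: "PK concentrations will be summarized by visit".

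The note after Table 2-1 makes the only exception for follow-up: "safety assessments in Week F60 in the post treatment follow-up period will NOT be mapped to Week 1" through Week 52. In the Week 60 row of Table 2-1, the weight/ECG and vital signs/laboratory columns say CRF visit, while the PK column gives days 394-449. SAP 2.8.3 repeats the CRF-visit approach for follow-up summaries, including early discontinuers, under a guideline for laboratory data, vital signs and ECG.

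When a window holds several values, Table 2-2 says "The measurement closest to the target will be used", with the first taken if two are equally distant. Its post-baseline rows are for efficacy and safety data; none names PK.

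Protocol 5.5.9 and the footnote to Table 6-1 ask early discontinuers to attend an end-of-treatment visit 4 weeks after the last dose and F60 a further 8 weeks later. Protocol Table 13-3 plans PK samples pre-dose at Weeks 4, 16 and 24, at 672 h post-dose at Week 52 and at 2016 h post-dose at Week 60.

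**The concern.** The exclusion does not reach PK on the documents' own classification. Protocol 6.5 lists the safety assessments, including immunogenicity, and PK is not among them. PK is in Protocol 6.6, Other assessments, and the SAP reports it in 2.9, outside 2.8 Safety analyses. Nothing else in the SAP holds an early discontinuer's F60 PK sample at the follow-up visit, so the day windows decide where it goes.

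PK in Japanese patients is a secondary objective. The by-visit concentration table is the PK summary that this SAP itself produces, because the population PK and PK/PD results are reported separately. In about 30 patients, a few samples from 84 days after the last dose could pull down a mean or geometric mean at Week 16, 24 or 52, and the table would not show why.

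**Working it through.** **Inputs**

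- Dosing visits (SAP 1.1): baseline, Weeks 1, 2, 3, 4, then every 4 weeks to Week 48. That is 16 visits, of which 15 come before Week 48.
- End of treatment (EOT) at last dose + 28 days; F60 at last dose + 84 days (Protocol 5.5.9). Table 13-3 agrees: 672/24 = 28 and 2016/24 = 84.
- PK windows (SAP Table 2-1): Week 4, days 2-71; Week 16, 72-141; Week 24, 142-267; Week 52, 268-393; Week 60, 394-449. Target days: 29, 113, 169, 365, 421.
- The column headings of Table 2-1 are broken in the text version. The PK column is taken to be the only one with windows at exactly Weeks 4, 16, 24, 52 and 60, which are the post-baseline visits in Table 13-3.

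**Formulas**

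Last-dose day d = 7 × week + 1; EOT day = d + 28; F60 day = d + 84.

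**Check against the plan's own figures**

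For a completer, d = 7 × 48 + 1 = 337. EOT = 337 + 28 = 365, and F60 = 337 + 84 = 421. These are the scheduled days of Weeks 52 and 60 in Table 2-1.

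**Early last doses, nominal timing**

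The last column gives the distance from target where another sample shares the window.

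| Last dose | d | EOT day (window) | F60 day (window) | F60 within its window |
|---|---|---|---|---|
| BSL | 1 | 29 (W4) | 85 (W16) | only sample |
| W1 | 8 | 36 (W4) | 92 (W16) | only sample |
| W2 | 15 | 43 (W4) | 99 (W16) | only sample |
| W3 | 22 | 50 (W4) | 106 (W16) | only sample |
| W4 | 29 | 57 (W4) | 113 (W16) | only sample, on target day |
| W8 | 57 | 85 (W16) | 141 (W16) | tie with EOT, 28 vs 28 |
| W12 | 85 | 113 (W16) | 169 (W24) | only sample, on target day |
| W16 | 113 | 141 (W16) | 197 (W24) | only sample |
| W20 | 141 | 169 (W24) | 225 (W24) | EOT closer, 0 vs 56 |
| W24 | 169 | 197 (W24) | 253 (W24) | Week 24 pre-dose closer, 0 vs 84 |
| W28 | 197 | 225 (W24) | 281 (W52) | only sample |
| W32 | 225 | 253 (W24) | 309 (W52) | only sample |
| W36 | 253 | 281 (W52) | 337 (W52) | F60 closer, 28 vs 84 |
| W40 | 281 | 309 (W52) | 365 (W52) | F60 closer, 0 vs 56; on target day |
| W44 | 309 | 337 (W52) | 393 (W52) | tie with EOT, 28 vs 28 |

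**Counts**

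- F60 is mapped to Week 16, 24 or 52 in 15 of 15. Week 60 starts on day 394, so it needs a last dose on day 394 − 84 = 310 or later.
- F60 is the only sample in its window in 9, where no selection rule could remove it.
- If the closest-to-target rule is applied to PK, F60 is also chosen in 2 more (Weeks 36 and 40), giving 11 of 15. The first-if-tied rule would choose EOT at Weeks 8 and 44. At Weeks 20 and 24, F60 is not chosen.

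**Off-schedule visits**

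EOT and F60 were each moved independently by −7 to +7 days (15 × 15 = 225 combinations per last-dose visit).

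- F60 stays in an earlier window in every combination for 14 of 15. The exception is Week 44, where F60 on day 394 or later is correctly Week 60.
- F60 stays the only sample in every combination for 8 of 9. The exception is Week 16, where EOT one day late (day 142) joins it in the Week 24 window.

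**Comparability**

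The planned pre-dose samples at Weeks 16 and 24 follow the Week 12 and Week 20 doses by 28 days, and the Week 52 sample is planned at 672 h. F60 is at 2016 h, and 2016/672 = 3 times as long.

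**The case against.** The best reply is that the SAP does not define safety assessments, and that SAP 2.1 sorts data into only two classes. Its text on interim cut-offs speaks of efficacy and safety variables, and Table 2-2 has only efficacy and safety rows after baseline, with an open-ended list of examples for safety. SAP 2.1.2 says the Table 2-2 conventions will be used whenever a window holds several measurements. PK has its own column in Table 2-1, so it must belong somewhere, and a serum concentration is not an efficacy variable. On that reading the note already covers PK and Table 2-2 already gives the selection rule. The PK Week 60 cell does not settle the matter by itself, because immunogenicity has the same cell and is covered by the note.

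That reading is possible, but the SAP does not state it, and it runs against the placing of PK in Protocol 6.6 and SAP 2.9. A programmer following the words as written would map F60 PK by day. If the two-class reading was intended, one sentence would say so.

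The points about scale stand. The counts are of hypothetical last-dose visits, and four of the nine only-sample cases are last doses at baseline or Weeks 1 to 3. The table is descriptive and no hypothesis is tested. SAP 2.9 lists every concentration, and Table 13-3 gives F60 its own sample number (106, against 103, 104 and 105 for Weeks 16, 24 and 52), so a misplaced value can be traced in the listing.

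**Conclusion.** The concern holds. As written, the SAP sends an early discontinuer's F60 PK sample to the Week 16, 24 or 52 window for every nominal last dose before Week 48. In 9 of those 15 cases F60 is the only sample in the window. The likely effect is to lower the concentration summaries at those weeks.

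This rests on three assumptions: that safety assessments means what Protocol 6.5 and SAP 2.8 list, that the PK column of Table 2-1 is identified correctly, and that visits fall near their nominal days. The number of patients affected cannot be derived. The documents give no discontinuation rate, F60 attendance after early discontinuation is worded as something patients should do, and those who withdraw consent have no further assessments. It may be zero.

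The consequence is confined to the by-visit PK table. The population PK model, the primary endpoint and the safety summaries are not affected. It should be corrected because the rule as stated gives wrongly labelled results and the correction is small.

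**What to change.** 1. In Table 2-1, set the PK Week 60 cell to CRF visit, as already done for weight/ECG and vital signs/laboratory data.
2. Extend the note after Table 2-1 to PK, so that F60 concentrations, including those of early discontinuers, are summarized only under the follow-up visit.
3. Add a PK row to Table 2-2 stating which sample is used when two fall in one window, and how ties are resolved.
4. Label the change as made after the Week 24 interim, which SAP 2.14 reports as already performed.

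The cost is one cell, one sentence and one table row, plus a re-run of the by-visit PK table if any early discontinuer attended F60. No new data are needed. The downside is that early discontinuers whose only sample in a window is F60 no longer count at Week 16, 24 or 52, so the table should show n at each visit.

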### **5.5.9      Discontinuation of study treatment**

Patients may voluntarily discontinue study treatment for any reason at any time.

They may be considered discontinued if they state an intention to withdraw, fail to return for visits, or become lost to follow-up for any other reason.

If premature discontinuation occurs for any reason, the investigator must make every effort to determine the primary reason for a patient's premature discontinuation from the study and record this information on the appropriate Study Phase Completion eCRF.

Patients who discontinue study should undergo an end of treatment visit (corresponds to the last visit for the patient's current period of treatment: e.g., Week 24, Week 52) at 4 weeks after last study treatment and then also return after an additional 8 weeks for a final follow-up visit, corresponding to Week F60 (12 weeks after last study treatment; see [Table 6-1](#)). The

final follow-up visit should be performed before any new treatment is initiated. For patients who are lost to follow-up (i.e., those patients whose status is unclear because they fail to appear for study visits without stating an intention to withdraw from the study), the investigator should show "due diligence" by documenting in the source documents steps taken to contact the patient, e.g., dates of telephone calls, registered letters, etc.

Patients who are prematurely discontinued from the study will not be replaced.

Study treatment must be discontinued under the following circumstances:

- Withdrawal of informed consent
- Emergence of the following adverse events:
  - a. Any severe or serious adverse event that is not compatible with administration of study medication, including adverse events that require treatment with prohibited co-medication
  - b. Onset of lymphoproliferative disease or any malignancy except for treated basal cell carcinoma, treated actinic keratoses, treated *in situ* carcinoma of the cervix or non-invasive malignant colon polyps which are being or have been removed
  - c. Life-threatening infection
  - d. Any laboratory abnormalities that in the judgment of the investigator are clinically significant and are deemed to place the patient at a safety risk for continuation in the study (A general guidance on clinically notable laboratory values is provided in [Appendix 1](#)).
  - e. Pregnancy
  - f. Use of any biologic immunomodulating agent except secukinumab

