2.1 Data analysis general information

The data will be analyzed by Novartis. SAS (version 9.4 or later) in GPSII will be used for all analyses in this SAP.

Summary statistics for continuous variables will include the number of patients (N), mean, standard deviation, minimum, median, maximum (lower quartile, upper quartile, if appropriate). Summary statistics for discrete variables will be presented in contingency tables and will include absolute and relative frequencies. The 95% confidence interval will be provided for efficacy variables as appropriate.

The cut-off date of the interim analysis at the applicable Week (e.g., Week 52) will be defined as the date of the last patient visit at the Week. All available data up to the cut-off date will be used in the interim analysis. The analysis results for efficacy variables by week will be presented only up to the applicable week (e.g., in case the Week 52 interim analysis, efficacy results at Week 60 will NOT be presented), while all available results from safety variables will be presented.

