2.5.3 Handling of missing values/censoring/discontinuations

Missing data for ASAS 20 up to Week 52 will be handled as follows:

1. Patients who drop out of the trial for any reason will be considered non-responders from the time they drop out
2. Patients who do not have the required data to compute response (e.g. ASAS components) at baseline and at the specific time point will be classified as non-responders.

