2.5.4 Supportive analyses

For binary efficacy variables, the percentage will be calculated based on the number of patients with an assessment at the analysis visits in the FAS (observed case analysis).

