2.7.3 Handling of missing values/censoring/discontinuations

These handlings for binary efficacy variables up to Week 52 will be the same as described in 2.5.3. For binary efficacy variables, the observed case analysis (the percentage calculated based on the number of patients with an assessment at the analysis visits in the FAS) is also performed as the supportive analysis.

Missing values for continuous efficacy variables will not be imputed. Summary statistics will be presented based on all data available at the analysis visits.

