2.8.3 Laboratory data

The general guideline for laboratory summaries(including Vital sign and ECGs) are as below:

- All the summary of lab outputs (newly occurring notables, maximum changes, shift tables, by visit summary statistics) will consider the "on-treatment" data, i.e., all assessments within last dose plus 84 days.

Follow up visit summary: using CRF visits (including early discontinued patients), i.e., not applying visit window and cut-off day 84. Summary of follow up visit outputs will be provided. The listing will provide follow up visit records.

- All records are displayed in the listing with the on-treatment flag, i.e., occurred within last dose plus 84 days- yes or no.

The summary of laboratory evaluations will be presented for three groups of laboratory tests (hematology, clinical chemistry, and urinalysis). In addition to the individual laboratory parameters the ratios "total cholesterol / HDL" and "apolipoprotein B / apolipoprotein A1" will be derived and summarized.

For urinalysis, frequency tables will be presented.

Descriptive summary statistics for the change from baseline to each study visit will be presented. These descriptive summaries will be presented by laboratory test and treatment group. Change

from baseline will only be summarized for patients with both baseline and post baseline values and will be calculated as:

$$\text{change from baseline} = \text{post baseline value} - \text{baseline value}$$

For each parameter, the maximum change (maximum decrease and maximum increase) from baseline, if appropriate for each study phase, will be analyzed analogously.

In addition, shift tables will be provided for all parameters to compare a patient's baseline laboratory evaluation relative to the visit's observed value. For the shift tables, the normal laboratory ranges will be used to evaluate whether a particular laboratory test value was normal, low, or high for each visit value relative to whether or not the baseline value was normal, low, or high. If appropriate, the shifts to the most extreme laboratory test value within entire treatment period will be presented as well (including category "high and low"). These summaries will be presented by laboratory test and treatment group.

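### The SAP keeps early stoppers' 12-week follow-up visit out of Weeks 1–52 for safety data only; their efficacy values from that visit are not excluded and by the literal rule land in Week 12 to Week 52 windows

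*SAP*

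**What the plan says.** Protocol 3.1, 5.5.9 and the footnote to Table 6-1 bring every patient back 12 weeks after the last dose. For early stoppers this visit corresponds to F60 and follows an end-of-treatment visit at 4 weeks.

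SAP 2.1.2 assigns data to analysis visits by day windows and adds: "The mapping described above applies to all visits (not just scheduled visits"). The note under Table 2-1 makes one exception: "safety assessments in Week F60 in the post treatment follow-up period will NOT be mapped to Week 1" through Week 52. In the Week 60 row, two columns (read as weight/ECG and vital signs/laboratory) are handled by CRF visit. The column for variables assessed at every visit, which include BASDAI, BASFI and hsCRP, has a day window of 394–449. For follow-up laboratory, vital sign and ECG summaries, SAP 2.8.3 works by "using CRF visits (including early discontinued patients), i.e., not applying visit window and cut-off day 84".

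The efficacy rules contain no condition on treatment status. For continuous variables (SAP 2.7.3), "Summary statistics will be presented based on all data available at the analysis visits". For the observed-case analysis (SAP 2.5.4), "the percentage will be calculated based on the number of patients with an assessment at the analysis visits in the FAS". If a window holds several efficacy values, Table 2-2 takes the one closest to the target day. The main binary analyses differ (SAP 2.5.3, applied to the secondary endpoints by 2.7.3): "Patients who drop out of the trial for any reason will be considered non-responders from the time they drop out".

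**The concern.** The SAP recognises that an early stopper's F60 visit does not belong in the on-schedule weeks, but it acts on this for safety data only. The same visit's efficacy values can then be reported as Week 16 or Week 52 results for secukinumab 150 mg, although the patient has had no dose for 12 weeks on a 4-weekly regimen. Nothing in the summary tables would identify them. The same patient could also be a Week 16 non-responder in the main table and a responder in the observed-case table. The Week 16 secondary endpoints and the by-week results support a filing and come from about 30 patients, so one patient is 1/30 = 3.3% of the sample. One patient weighs more in the subgroups of SAP 2.2.1.

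**Working it through.** **The plan's own figure.** SAP section 3 gives a lower 95% limit of about 42.5% for 30 patients and a 60% response. The Wald formula reproduces it: 0.60 − 1.96 × √(0.60 × 0.40/30) = 0.425. The point does not depend on this figure; it only supplies N = 30 and 18 expected responders.

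**Is efficacy measured at F60?** The efficacy rows of protocol Table 6-1 are not in the text available. The SAP implies that it is: Table 2-1 gives these variables a Week 60 window, and SAP 2.1 says that in the Week 52 interim "efficacy results at Week 60 will NOT be presented".

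**Where does F60 fall?** Day of last dose = 7 × week + 1, and F60 day = day of last dose + 84. The windows are those for variables assessed at every visit, with visits on schedule.

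| Last dose | F60 day | Window |
|---|---|---|
| Baseline, Week 1, Week 2 | 85, 92, 99 | Week 12 (72–99) |
| Week 3, Week 4 | 106, 113 | Week 16 (100–127) |
| Week 8 | 141 | Week 20 (128–155) |
| Week 12 | 169 | Week 24 (156–183) |
| Weeks 16 to 36, every 4 weeks | 197 to 337 | Weeks 28 to 48 |
| Week 40, Week 44 | 365, 393 | Week 52 (352–393) |
| Week 48 | 421 | Week 60 (394–449) |

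So 15 of the 16 possible last-dose visits put F60 inside Weeks 12–52. Days 99 and 393 are the last days of their windows, so a visit one day late would move to Week 16 or Week 60 respectively.

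**Does another value displace it?** The end-of-treatment visit is at last dose + 28 days. For a last dose at Week 3 or 4 that is Day 50 or 57 (Week 8). For Week 40 or 44 it is Day 309 or 337 (Week 44 or 48). F60 is therefore the only scheduled value in its Week 16 or Week 52 window, and the closest-to-target rule does not remove it.

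**SF-36 and ASQoL.** The columns of Table 2-1 are broken in the text. If, by elimination, the 100–141 entry is their Week 16 window, a last dose at Week 8 (F60 on Day 141) also feeds Week 16 for these two endpoints.

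**Size, observed-case ASAS 20 at Week 16.** Assume k = 1 to 3 affected patients and 18 responders among the others. Kept out, the rate is 18/(30 − k). Mapped in, it runs from 18/30 (none of the k responds) to (18 + k)/30 (all respond).

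| k | Kept out | Mapped in | Difference, points |
|---|---|---|---|
| 1 | 18/29 = 62.1% | 60.0% to 63.3% | −2.1 to +1.3 |
| 2 | 18/28 = 64.3% | 60.0% to 66.7% | −4.3 to +2.4 |
| 3 | 18/27 = 66.7% | 60.0% to 70.0% | −6.7 to +3.3 |

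**Size, mean BASDAI change.** If the k values lie d points from the mean of the others and all 30 are observed, the mean shifts by k × d/30. For d = 1 to 4 (assumed), the shift is 0.03 to 0.13 for one patient and 0.10 to 0.40 for three.

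**The case against.** No sentence in the SAP says that F60 efficacy values go into Weeks 12–52. That follows from a general mapping rule and an exception that names only safety. This stands, and it is why the point is worded as not excluded. The SAP 2.1 statement on Week 60 results does not close the gap: it concerns the Week 60 analysis visit, not a value already mapped to an earlier week.

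The SAP's only on-treatment limit is last dose plus 84 days, and an on-schedule F60 visit falls exactly on it. This also stands. An on-treatment filter as the SAP defines it would not remove these values, so the remedy has to be the visit rule.

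Using all available data after discontinuation can be a legitimate choice. But the SAP does not state it as one, and it handles the same visit differently for safety. Exclusion is not neutral either: if none of these patients responds, it raises the observed-case rate.

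A reader might infer that the values usually reflect another drug. The documents do not support that. Protocol 5.5.9 says the "final follow-up visit should be performed before any new treatment is initiated", and 5.5.6 bars rescue before the Week 16 assessments are complete. Exposure remains possible, for example after biologic rescue, which itself ends participation, or with the non-biologic care that 5.5.13 allows. That is not enough to support a protocol change.

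**Conclusion.** The gap is real and small. It affects the continuous summaries (BASDAI and hsCRP, probably SF-36 PCS and ASQoL) and the supportive observed-case percentages, in a descriptive study without hypotheses. For BASDAI and hsCRP at Week 16 it needs a patient whose last dose was at Week 3 or 4 and who still attends 12 weeks later. Patients who withdraw consent have no further assessments. The number of early stoppers is not given; one to three is an assumption, and three is not supported by anything in the documents. The direction is unknown.

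A reader might infer that the primary ASAS 20 result is affected. It is not, provided drop-out is dated at discontinuation, because such patients are then non-responders whatever was recorded at F60. The SAP does not define that date, but the protection extends to the main analysis of every binary secondary endpoint on the same reading.

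**What to change.** Extend the note under SAP Table 2-1 to efficacy and patient-reported assessments at F60. Change their Week 60 entry from days 394–449 to CRF visit, so that they are summarised separately, as SAP 2.8.3 already does for safety. Keep the values in the listings and leave the 84-day safety limit as it is. With F60 kept out, an early stopper would also have no value in the window, so the missing-data rule of 2.5.3 gives non-response however drop-out is dated.

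The Week 24 interim has already been run in an open-label trial. The SAP should therefore record the change as made after that interim and show any Week 16 or Week 24 values that differ.

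The cost is a short SAP edit, a programming change to the visit mapping and a re-run of the affected tables. No new data and no protocol amendment are needed. The downside is that a few off-drug values leave the by-week summaries; they remain in the F60 summary and listings.
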